2. LAY SUMMARY

The six-minute walk test (6MWT) is a standard method for measuring exercise capacity in patients with cardiopulmonary disease such as pulmonary hypertension (PAH) and measures how far a patient can walk in 6 minutes. The test is usually performed in the hospital, by walking along a hospital corridor. Since the outbreak of SARS-CoV-2, there has been a need to minimise patient contact with hospitals and their staff to reduce transmission of the virus. In a previous research project called 6APP, we designed, developed and evaluated a mobile phone app, to allow them to perform the 6MWT in the community. Given the current circumstances, cardiovascular outpatients including patients in the PHT clinic in Oxford are being recommended to use an app derived from that project to provide their 6MWT distance to the clinical team for assessment, in addition to their symptoms and general well-being. This is felt to be more appealing to the patients, and would reduce the time spent in hospital on the day of their outpatient appointment.

We would like to measure the usefulness of adopting remote, mobile-based 6MWT among hospital outpatients, within the constraints imposed by the SARS-COV2 pandemic.

3. SYNOPSIS

The Trial will review the use of a mobile-based 6MWT by hospital outpatients during the coronavirus pandemic and evaluate its use

Trial Title	Evaluation of the usefulness of adopting remote, mobile-based 6MWT among hospital outpatients (the 6-APP now Study), within the constraints imposed by the SARS-COV2 pandemic.		
Internal ref. no. (or short title)	6-APPnow Study		
Trial registration	Clinical Trials. gov		
Sponsor	Oxford University Hospitals NHS Foundation Trust [name]		
Funder	NIHR BRC and the Swedish Knowledge Foundation		
Trial Design	Patient survey to evaluate their use of the 6 minute walk test smartphone app as a surrogate for regular clinic 6MWT.		
Trial Participants	Patients using 6 minute walk tests for managing cardiopulmonary function or disease management		
Sample Size	250-500 patients attending the outpatient clinics		
Planned Trial Period	Q2 2021 – Q2 2022		
Planned Recruitment period	Q2 2021 – Q2 2022		
	Objectives	Outcome Measures	Timepoint(s)
Primary	To assess whether patients are able and willing to use a smartphone app for the 6MWT	Percentage of participants who perform at least one app-based 6MWT before patient consultation.	At 3, 6, 9 and 12 months after the start of the study.
Secondary	
To assess the accuracy of the app-based measurement.
 
To assess whether differences in distance walked altered management of patients.
	
Measurement of walked distance (6MWD) measured by the app compared with a trundle wheel reference.
 
Number of clinical investigations and multidisciplinary team discussion triggered by variations in app-based 6MWD.
	
12 months
 
At 3, 6, 9 and 12 months after the start of the study.

	
To assess the usability and acceptance of the app.
 
To collect raw data from phones' sensors to allow the development of future algorithms for app-guided 6MWT.
 
To determine whether the use of the 6MWT reduces time spent and number in hospital visits.
 
To compare the use of 6MWT during pandemic with pre-pandemic use.
	
Standard usability and acceptance questionnaires, semi-structured interviews.
 
Localisation position (GPS), speed, acceleration, step count, gyroscope samples collected during 6MWT.
 
Time spent in hospital attendances and number of hospital visits made during use of the 6MWTapp compared with previous periods.
 
Total number of 6MWTS performed during 2020 pandemic period compared with pre-pandemic period.
	
12 months
 
12 months
 
12 months
 
12 months

--	---	---	---

4. ABBREVIATIONS

AE	Adverse event
AR	Adverse reaction
CI	Chief Investigator
CRA	Clinical Research Associate (Monitor)
CRF	Case Report Form
CRO	Contract Research Organisation
CT	Clinical Trials
CTA	Clinical Trials Authorisation
CTRG	Clinical Trials and Research Governance
DMC/DMSC	Data Monitoring Committee / Data Monitoring and Safety Committee
FC	Functional capacity
GCP	Good Clinical Practice

GP	General Practitioner
ICF	Informed Consent Form
NHS	National Health Service
NRES	National Research Ethics Service
NYHA	New York Heart Association
OUH	Oxford University Hospitals
PAH	Pulmonary arterial hypertension
PH	Pulmonary hypertension
PI	Principal Investigator
PIL	Participant/ Patient Information Leaflet
R&D	NHS Trust R&D Department
REC	Research Ethics Committee
SOP	Standard Operating Procedure
VO2 Max	Maximal oxygen consumption on exercise test
6MWD	Six minute walk distance
6MWT	Six minute walk test
SUSAR	Suspected Unexpected Serious Adverse Reactions
TMF	Trial Master File
TSG	Oxford University Hospitals NHS Foundation Trust / University of Oxford Trials Safety Group

5. BACKGROUND AND RATIONALE

5.1. Telemedicine in the context of COVID19

Since the outbreak of SARS-CoV-2, health care systems have been subject to increased pressures. This is mainly due to infected patients being admitted to the medical wards and intensive care units, but also due to the requirement to reduce exposure of both healthcare professionals and patients to COVID by minimising contact.

There are indications that reduced access to healthcare services during the pandemic is responsible for more than half of excess deaths in the United States¹. In response to this, the CDC is advocating the use of telemedicine to keep providing a remote version of healthcare services². A study of telemedicine

¹ <https://jamanetwork.com/journals/jama/fullarticle/2768086>

² <https://www.cdc.gov/coronavirus/2019-ncov/hcp/telehealth.html>

services in China used during COVID-19 pandemic showed that they reduced burden on hospitals, prevented overcrowding, reduced the risk of cross-infection, and relieved patients' anxiety³. The use of telemedicine is also being developed in Europe, where many patients are being denied the use of clinical services, like cardiac rehabilitation⁴, because of centres being closed. In the context of the NHS, an increased use of telemedicine services is being observed⁵. The NHS long-term plans do, in fact, include tele-consultations as a pillar for its sustainability⁶. Healthwatch have produced useful advice for outpatient clinicians to consider avoiding asking patients to attend physical outpatient appointments where a clinically-appropriate and accessible alternative exists. Where an appointment is clinically necessary, the national benchmark is that at least 25% could be conducted by telephone or video including 60% of all follow-up appointments. Initial promising results are being seen in the context of diabetes, where virtual clinics are recommended as mitigation to the pandemic⁷.

5.2. The 6MWT

To assess patient's exercise capacity, the six-minute walk test (6MWT) is a standard method used in patients with cardiopulmonary disease such as Heart Failure (HF) or Pulmonary arterial Hypertension⁸ (PAH). The 6MWT measures how far a patient can walk in 6 minutes. Walking is an activity performed every day, by most patients except for those most severely limited. By assessing patients' ability to exercise, the 6MWT provides a global assessment of respiratory, cardiovascular, neuromuscular and cognitive function. The 6MWT does not differentiate what limits the patient, nor does it assess maximal exercise capacity. Instead, the 6MWT allows the patient to exercise at a daily functional level, and is a useful tool for assessing changes after a therapeutic intervention, and correlates with a subjective improvement in dyspnoea⁹.

In PAH the 6MWT is used to evaluate patients' response to treatment, with an increase in 6MWT distance of greater than 42 m being considered a clinically significant improvement¹⁰. Furthermore, change in 6MWT distance correlates with VO2 max, NYHA class and mortality in those patients, providing an objective assessment of disease progression, prognosis and response to treatment. It is a universally accepted test as it is safe and easily performed by the patient.

5.3. Cardiovascular outpatient management during the pandemic

³ <https://mhealth.jmir.org/2020/7/e19417/>

⁴ <https://clinowl.com/the-future-is-now-a-call-for-action-for-cardiac-telerehabilitation-in-the-covid-19-pandemic-from-the-secondary-prevention-and-rehabilitation-section-of-the-european-association-of-preventive-cardiolo/>

⁵ <https://digital.nhs.uk/coronavirus/nhs-digital-tech-analytics>

⁶ <https://www.bmjjournals.org/content/364/bmj.l84.long>

⁷ <https://www.jmir.org/2020/8/e21609/>

⁸ <https://pubmed.ncbi.nlm.nih.gov/12890299/>

⁹ <https://www.ahajournals.org/doi/full/10.1161/circulationaha.112.105890>

¹⁰ <https://www.atsjournals.org/doi/full/10.1164/rccm.201203-0480oc>

Since the outbreak of SARS-CoV-2, the standard regime of care for outpatients with cardiovascular disease has been affected.

For example, in PAH patients, the normal regime of a 6MWT, echocardiogram and face to face consultation was abandoned as those patients were felt to be extremely clinically vulnerable, and therefore were recommended to shield at home. Therefore patients needed to be assessed without having any face to face contact, unless in an emergency. This situation continued for five months until August, when shielding was initially withdrawn, however we are now back in this situation with a highly transmissible variant SARS-CoV-2. Therefore the need to reduce time spent in hospital continues as the virus continues within the community.

In cardiovascular outpatient clinics in Oxford, patients are now being regularly contacted by phone to replace face to face visits. During these phone calls, questions about the general status of the patient are asked, i.e. how far they think they can walk and whether they have noticed a change in their exercise capacity or functional capacity, but currently no objective data, like the results of the 6MWT, are available for assessment.

5.4. Telemedicine services for pulmonary hypertension

In a previous research project called 6APP, we designed, developed and evaluated a mobile-health “app” (a type of telemedicine where patients use their mobile phones), to allow them to perform the 6MWT in the community. We hypothesized that a test conducted by patients, in their environment, would reflect more the patient’s functional status, would free up healthcare resources and would be less stressful and costly for the patients themselves.

The app allowed patients to perform the test both indoors, by walking back and forth along a corridor of fixed length, and outdoors, using the localization system (like the GPS). In our study with 30 PAH patients, we proved that the app is accurate when used outdoors, the measurements are reliable and repeatable and the method is well-accepted by patients¹¹.

After these encouraging results, the app has been simplified and made available for free for both Android and iPhones under the name of “Timed Walk”. The original app was developed by [name] at the Institute of Biomedical Engineering of the Oxford University. The current app, which uses the same validated outdoors test approach, is instead maintained by the University of Malmo, Sweden, where [name] is currently employed.

Given the current circumstances, the PH clinic in Oxford and other cardiovascular outpatient clinics are recommending patients to use the Timed Walk app, the results of which are being used by the clinical team to assess patients in addition to their symptoms and general well-being. This is felt to be more appealing to the patients, and would reduce the time spent in hospital on the day of their outpatient appointment. The app only allows outdoor tests (as these proved to be more reliable and practical) and to share 6MWT data via email if patients want to.

¹¹ <https://mhealth.jmir.org/2020/1/e13756/> and <https://preprints.jmir.org/preprint/22748>

It has to be noted that the app is only used to identify trends and, when deterioration is detected, for example reduction in 6MWT distance walked or change in Borg score, patients are invited to the clinic for further assessment.

6. OBJECTIVES AND OUTCOME MEASURES

The population to be studied is composed of hospital outpatients who have conditions where the 6MWT is routinely used in clinical care, and/or are using the 6APP as an alternative.

The objective is: To evaluate the usefulness of adopting remote, mobile-based 6MWT among hospital outpatients, within the constraints imposed by the SARS-COV2 pandemic.

Objectives	Outcome Measures	Timepoint(s) of evaluation of this outcome measure (if applicable)
Primary Objective To assess whether patients are able and willing to use a smartphone app for the 6MWT	Percentage of participants who perform at least one app-based 6MWT before patient consultation.	At 3, 6, 9 and 12 months after the start of the study.
Secondary Objectives To assess the accuracy of the app-based measurement. To assess whether differences in distance walked according to the app altered management of patients.	Comparison of walked distance (6MWD) measured by the app versus a trundle wheel reference. Number of clinical investigations and multidisciplinary team discussion triggered by variations in app-based 6MWD.	12 months. At 3, 6, 9 and 12 months after the start of the study.

To assess the usability and acceptance of the app.	Standard usability and acceptance questionnaires, semi-structured interviews.	12 months.
To collect raw data from phones' sensors to allow the development of future algorithms for app-guided 6MWT.	Localisation position (GPS), speed, acceleration, step count, gyroscope samples collected during 6MWT.	12 months.
To determine whether the use of the 6MWT reduces time spent and number in hospital visits.	Time spent in hospital attendances and number of hospital visits made during use of the 6MWT compared with previous periods.	12 months.
To compare the use of 6MWT during pandemic with pre-pandemic use.	Total number of 6MWTS performed during 2020 pandemic period compared with pre-pandemic period.	12 months.

7. TRIAL DESIGN

The study consists of 2 parts. The first consists of collecting data about the use of an app for phone-based 6MWT, the “Timed Walk” app, during the outpatient consultations (via phone or in clinic). These data will be used to understand if patients are using the app and if the measurements produced by the app are being used for clinical decisions. The data will be collected on an electronic spreadsheet, using a coding schema, which will be analysed every 3 months for quality assurance and at the end of the study for the final statistics.

The second part of the study will involve a sample of 15 patients who will be sent a trundle wheel and will be invited to perform 10 6MWT using the app and the trundle wheel simultaneously. The data collected in this way will be used to A) assess the accuracy of the app measurement and B) create a public anonymised dataset for the development of future algorithms for the 6MWT. The same group of patients will also be invited to answer a questionnaire about the usability and acceptance of the app and will be interviewed about the same topics.

This study is a collaboration between the Oxford University Hospital (OUH) Trust and Malmo University, Sweden. Malmo University is the main developer and maintainer of the Timed Walk app, and their interest focuses on the accuracy and usability of the app. The OUH Trust is, on the other hand, interested in using the app to remotely monitor their cardiac patients and assessing its impact on the management of those patients. Malmo University will therefore offer engineering work both in terms of the app and data analysis and OUH will recruit patients and collect data.

8. PARTICIPANT IDENTIFICATION

8.1. Trial Participants

All patients under the care of the cardiovascular clinics in Oxford, who are able to walk and use a smartphone.

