8.2. Inclusion Criteria

- Participant is willing and able to give informed consent for participation in the study.
- Male or Female, aged 18 years or above.
- Under the care of the cardiovascular clinic at OUH Owning or having access to a smartphone with either Android or iOS
- Being able to use a smartphone app
- Being able to walk

A subgroup of 15 patients will be identified among those who are more willing to use the app to perform the additional measurements with the trundle wheel and to answer the questionnaire. This group should include a balanced representation of age groups and sexes.

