8.3. Exclusion Criteria

The participant may not enter the study if ANY of the following apply:

- Long term oxygen therapy
- Cognitive impairments
- Cannot use a smartphone
- Pregnancy
- Not able to complete a 6MW

- Any other significant disease or disorder which, in the opinion of the Investigator, may either put the participants at risk because of participation in the trial, or may influence the result of the trial, or the participant's ability to participate in the trial.

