9. TRIAL PROCEDURES

9.1. Recruitment

Outpatients undergoing follow up in the cardiovascular outpatient clinics in Oxford will be eligible for participation. Some of these patients are already using the app, regardless of the study, for example in the case of the pulmonary hypertension clinic. They will be approached by a member of the clinical team for consideration and recruited during a regular consultation either via phone call or during a visit in the clinic. They will be asked to download the app over the Internet.

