9.2. Screening and Eligibility Assessment

Patients will be screened every week according to the scheduled clinic phone calls or visits. A list of candidates who match inclusion and exclusion criteria (except use of smartphone) will be prepared before consultation.

During the consultation, patients will be asked about their access and fluency with smartphones to further verify compliance with the criteria.

The subgroup of 15 patients will be chosen among those using the app depending on the frequency of their use of the app and general willingness to participate in the study.

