9.1. Enrolment

All eligible patients will be enrolled from outpatient clinics. They will be recruited to the trial and not randomised .

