12.2. Sample Size Estimation

For part 1, we will not use sampling as we aim to involve all patients in the cardiovascular clinics who require a 6MWT and are able to use the app.

With regards to part 2, our 15 patients cohort is in agreement with typical usability studies.

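### No entry criterion requires a clinical need for the 6MWT, although section 12.2 and the synopsis describe patients who need or use it, so the primary denominator and the pre-pandemic comparison are ambiguous

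*Combined protocol and SAP*

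**What the plan says.** The document describes its population in two ways.

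The operative text is wide. Section 8.1 (Trial Participants) takes "All patients under the care of the cardiovascular clinics in Oxford, who are able to walk and use a smartphone". Section 8.2 adds consent, adult age, clinic care, smartphone access, and the ability to use an app and to walk. The one exclusion in 8.3 that mentions the test, "Not able to complete a 6MW", concerns ability and not need. Section 9.1 (Recruitment) says "Outpatients undergoing follow up in the cardiovascular outpatient clinics in Oxford will be eligible for participation". Section 9.2 (Screening and Eligibility Assessment) says "A list of candidates who match inclusion and exclusion criteria (except use of smartphone) will be prepared before consultation". Section 9.1 (Enrolment) says "All eligible patients will be enrolled from outpatient clinics".

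The text on aims is narrower. Section 12.2 sets the target for part 1 as "all patients in the cardiovascular clinics who require a 6MWT and are able to use the app". The synopsis describes patients whose cardiopulmonary condition is managed with the help of walk tests. Section 6 describes "hospital outpatients who have conditions where the 6MWT is routinely used in clinical care", and the same sentence then adds, joined by and/or, patients who use the app in its place.

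The analysis follows the wide text. The primary outcome is a percentage of participants, section 12.1 computes it from each recruited patient, and section 12.3 analyses every participant. Section 12.1 also compares the number of 6MWTs per patient in the study period with the previous 5 years. For that comparison, section 9.2 (Baseline Assessments) draws only patient ID and test date from the health record. The event log in section 9.3 (Subsequent Visits) has codes for app tests and for clinic tests, but none for whether the 6MWT is part of the patient's care.

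**The concern.** The primary objective asks whether patients are able and willing to use the app. A participant who has no clinical reason for a 6MWT may simply not do one, and would then count against the app in the same way as someone who could not or would not use it. The reported percentage would mix two different things, and a reader could not tell how much of each.

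The comparison with pre-pandemic use has a related problem. A participant for whom the test was never part of care brings no clinic tests from the earlier years. Whether that person raises or lowers the apparent change depends on who is counted in the earlier period, which the plan does not fix.

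The two groups could not be cleanly separated afterwards. The 5-year record pull shows who had a clinic test before. It does not identify a newly referred patient who has a real indication but no past test. Section 5.3 adds to this: it reports that the usual regime, including the 6MWT, was suspended for pulmonary arterial hypertension patients during the pandemic.

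**Working it through.** **Is there a figure to reproduce?** The synopsis gives 250 to 500 patients. It has no stated expected rate, precision or power, and section 12.2 says part 1 does not sample. There is nothing to reproduce. The range is used below only to set the scale of sampling error.

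**Primary percentage.** Let *f* be the share of participants with no 6MWT need, and *p1* and *p0* the uptake with and without need. The documents give none of these three, so all are assumptions.

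- Observed percentage = (1 − *f*) × *p1* + *f* × *p0*.
- Shift from the figure for patients with need = *f* × (*p0* − *p1*).

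With *p1* = 60% and *p0* = 10%:

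- *f* = 20%: 0.8 × 60 + 0.2 × 10 = 48 + 2 = 50%.
- *f* = 40%: 0.6 × 60 + 0.4 × 10 = 36 + 4 = 40%.

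With *p1* = 70% and a range for *p0*:

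| *f* | *p0* = 70% | 35% | 10% | 0% |
|---|---|---|---|---|
| 0% | 70.0 | 70.0 | 70.0 | 70.0 |
| 10% | 70.0 | 66.5 | 64.0 | 63.0 |
| 30% | 70.0 | 59.5 | 52.0 | 49.0 |

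The shift is zero along the first row and down the first column. Restricting the denominator to patients with need returns 70% in every cell.

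**Against sampling error.** The 95% half-width is 1.96 × √(*p*(1 − *p*)/*n*). At *p* = 70% it is 1.96 × √(0.21/250) = 5.7 points for 250 patients and 1.96 × √(0.21/500) = 4.0 points for 500. The shift equals the half-width when *f* = half-width / (*p1* − *p0*):

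| *n* | *p0* = 35% | 10% | 0% |
|---|---|---|---|
| 250 | 16.2% | 9.5% | 8.1% |
| 500 | 11.5% | 6.7% | 5.7% |

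Under these assumptions, a share of roughly 6 to 16% without need would be enough for the shift to match sampling error.

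**Pre-pandemic comparison.** Assume that patients with need have 2 tests per year in both periods, so the true change is nil. Assume also that *f* = 30%, and that the others had 0 tests before and have *x* app tests per year now, with *x* from 0 to 2. The rate during the study is 0.7 × 2 + 0.3 × *x*, which runs from 1.4 to 2.0.

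- Same participants counted in both periods: the earlier rate is 0.7 × 2 = 1.4. The difference is 0 to +0.6 and the ratio 1.00 to 1.43.
- Only patients with a recorded 6MWT counted in the earlier period: the earlier rate is 2. The difference is −0.6 to 0 and the ratio 0.70 to 1.00.

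With no true change, one choice of denominator can show a rise and the other a fall. The plan is compatible with both.

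**The case against.** The strongest reply is that this is loose wording in a descriptive study with no planned hypothesis test. Section 6 expressly admits app users alongside patients for whom the test is routine, and its overall objective concerns hospital outpatients in general. Members of the clinical team make the approach, section 12.2 tells them whom the study is for, and everyone enrolled has consented to a study of a walk-test app. The record pull already flags participants with a previous clinic test.

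Much of this stands, and it rules out four stronger readings that a reader might infer.

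- That any cardiovascular clinic patient may enter. The other criteria in 8.2 and 8.3 still apply; what is missing is a condition on need.
- That the objectives confine the study to patients who need the test. The and/or clause in section 6 prevents that; only 12.2 states need outright, with the synopsis close to it.
- That the primary figure will be 10 to 20 points too low. Those differences come entirely from assumed uptake and shares, and nothing in the documents shows that uptake differs by indication.
- That the use comparison will show a false rise. It could as easily show a false fall.

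Nor do the documents say that screening lists are applied without clinical judgement. Equally, no passage gives the clinical team a filter on need, and the aim stated in 12.2 is not carried into any criterion. The mismatch therefore remains, and it reaches the analysis through 12.3.

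**Conclusion.** The point holds as an inconsistency with a possible effect on two results. The entry text never requires a 6MWT need, three other places describe a population defined at least partly by it, and no passage reconciles them. Enrolling by the criteria as written can put patients with no reason for the test into the primary denominator, with no recorded item to identify them.

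The size cannot be known from the documents. Dilution of the primary percentage requires both that such patients enrol and that they use the app less. The 50% and 40% illustrations rest on the assumed 60% and 10% uptake and on the assumed 20% and 40% shares. The direction of any bias in the pre-pandemic comparison stays open until its denominator is defined. The change is worth making before enrolment, because indication cannot be fully reconstructed later.

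**What to change.** - Reconcile 8.1 and 8.2 with section 6 and 12.2, so that one definition of the population is used throughout. If the wider group is intended, including app users without a routine indication, say so in 12.2 and the synopsis.
- Record at enrolment one yes/no item: is the 6MWT part of this participant's care? Count as yes a previous clinic 6MWT in the record or one requested by the clinic team, so that newly referred patients are not missed.
- In 12.1 and 12.3, report the primary percentage for the 6MWT-indicated group as the main result, with all participants alongside.
- Make the use comparison in the same 6MWT-indicated patients in both periods, counting only time under clinic care.

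The cost is one extra recorded item and a somewhat smaller main denominator. For example, if 20% of 250 participants had no indication, 250 × 0.8 = 200 would remain. At an assumed 60%, the 95% half-width would go from 1.96 × √(0.24/250) = 6.1 points to 1.96 × √(0.24/200) = 6.8 points. Counting time under clinic care also needs the date on which each patient came under the clinic, which the planned record pull of ID and test date does not include. No participant has to be turned away if the wider group is kept.
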